### 6.3.2 Youth Randomized Trial: Pre-Entry Visit

Pre-Entry procedures for the Randomized Trial are targeted to be conducted on the same day of the Entry Visit with an allowable window of up to 14 days prior to the Entry Visit (refer to [Sections 6.3.3](#) and [6.3.4](#)).

Youth Pre-Entry Visit Procedures for Randomized Trial (up to 14 days prior to enrollment)		
Clinical		
 
Obtain targeted medical/medications history per Section 6.5 If applicable, ascertain gender identity
 

Behavioral and Counseling		
 
Administer electronic questionnaires - pen and paper may be substituted per Section 10.1: Baseline measures:               
 
Disclosure
 
Self-report ART Adherence
 
Barriers to adherence
 
Gender-based Violence (WHO – Victim/Perpetrator)
 
Gender Roles (Rachel Jewkes)
 
AIDS-Related Stigma Scale
 
AIDS Risk Behavior Assessment (Sexual behavior/Drug and alcohol use)
 
Children’s Report of Parenting Behavior Inventory
 
 
 

Laboratory	Blood	
 
Collect blood for (baseline measures):               
 
HIV-1 RNA (viral load test)
 
Plasma for Inflammatory biomarkers
 
 
 

	Hair	
 
Hair sample (50-60 strands) for ART concentration (baseline measure) – to be collected from the head (scalp) only; not required if participant is bald
 

Gender identity should be ascertained at the Pre-Entry visit; however, this procedure should not be performed at sites that have formally opted out of collection of gender identity data, in accordance with policies specified in the IMPAACT Manual of Procedures. Gender identity data should be collected from participants in private, without their parent or guardian present.

### 6.3.3 Youth Randomized Trial: Entry Visit

The pool of 12-20 eligible youth who completed Pre-Entry Visit procedures will complete their Entry Visit on the same day as the first group session. Eligible youth will be enrolled and randomized during the Entry Visit.

Youth Entry Visit Procedures for Randomized Trial (same day as Group Session 1)	
Administrative and Regulatory	
 
Confirm final eligibility determination
 
Complete paper-based eligibility checklist for Step 2, enter checklist data into SES to enroll/randomize the youth, print and file a copy of the confirmation file
 

### 6.3.4 Youth Randomized: Group Sessions 1-6 Study Visits

Group Session 1 for the TI-CBT and Discussion Control arms are targeted to occur on the day when group members complete their study Entry Visits and are randomized to either the TI-CBT Intervention Arm or the Discussion Control Arm. Every effort will be made to keep the TI-CBT and Discussion Control groups separated once youth are randomized to an arm (e.g., group sessions occur in separate buildings, group sessions' start times staggered so one group leaves before the other finishes, etc.)

All six group sessions within an arm should be completed within eight weeks of the date of Group Session 1. Group sessions may be conducted on separate days or multiple sessions may be conducted on the same day.

Youth Group Sessions 1-6 Procedures for Randomized Trial (within 8 weeks of Group Session 1)	
Behavioral and Counseling	
 
IYL-delivered youth TI-CBT or Discussion Control group session [refer to Section 5.1]
 
Administer after each group session: Two questions on “Amount of fun had” and “Amount learned” [refer to Section 5.5.4]
 

### 6.3.5 Youth Randomized Trial: Immediately Post-Last group session Follow-up Study Visit

The Immediately Post-Last group session (IPL) Follow-up Study Visit is targeted to take place immediately following the last group session, either on the same day or within a targeted window of up to 14 days and an allowable window of up to 30 days following the last group session.

Youth Immediate Post-Last group session (IPL) Follow-up Study Visit Procedures for Randomized Trial (up to 30 days following the last group session)		
Clinical		
 
Obtain targeted medical/medications history per, Section 6.5
 

Behavioral and Counseling		
 
Administer electronic questionnaires - pen and paper may be substituted per Section 10.1: 
 
Participant Intervention Evaluation [refer to Section 5.5.4]
 
PHQ-9
 
GAD-7
 
UCLA PTSD-RI
 
Self-reported ART Adherence
 
Barriers to adherence
 
Gender-based Violence (WHO – Victim/Perpetrator)
 
Gender Roles (Rachel Jewkes)
 
AIDS-Related Stigma Scale
 
AIDS Risk Behavior Assessment (Sexual behavior/Drug and alcohol use)
 
Children’s Report of Parenting Behavior Inventory
 
 
 

Laboratory	Blood	
 
Collect blood for: 
 
HIV-1 RNA (viral load test)
 
 
 

	Hair	
 
Hair sample (50-60 strands) for ART concentration – to be collected from the head (scalp) only; not required if participant is bald
 

### 6.3.6 Youth Randomized Trial: 6 Month Follow-up Study Visit

The 6 Month Follow-up Study Visit is targeted to take place on Day 182, counted from the day of the first group session as Day 0, with a targeted window of  $\pm 14$  days and an allowable window of  $\pm 30$  days.

Youth 6 Month Follow-up Study Visit Procedures for Randomized Trial ( $\pm 30$ days)		
Clinical		
 
Obtain targeted medical/medications history per Section 6.5
 

Behavioral and Counseling		
 
Administer electronic questionnaires - pen and paper may be substituted per Section 10.1:               
 
PHQ-9
 
GAD-7
 
UCLA PTSD exposure screener and reaction index
 
Self-report ART Adherence
 
Barriers to adherence
 
Gender-based Violence (WHO – Victim/Perpetrator)
 
Gender Roles (Rachel Jewkes)
 
AIDS-Related Stigma Scale
 
AIDS Risk Behavior Assessment (Sexual behavior/Drug and alcohol use)
 
Children’s Report of Parenting Behavior Inventory
 
Risk for Contamination
 
 
 

Laboratory	Blood	
 
Collect blood for:               
 
HIV-1 RNA (viral load test)
 
Plasma for Inflammatory biomarkers
 
 
 
Hair sample (50-60 strands) for ART concentration – to be collected from the head (scalp) only; not required if participant is bald
 

### 6.3.7 Youth Randomized Trial: 6 Month Booster Group Session Study Visit

The 6 Month Booster Group Session should take place after completion of the 6 Month Follow-up Study Visit evaluations. For each participant in a group, the booster group session is targeted to take place on the same day (Day 182) as the 6 Month Follow-up Visit with a targeted window of up to 14 days and an allowable window of up to 30 days following the 6 Month Follow-up Study Visit.

Youth 6 Month Booster Group Session Procedures for Randomized Trial (up to 30 days following the 6 Month Follow-up Study Visit)	
Behavioral and Counseling	
 
Booster Group Session: IYL-delivered youth TI-CBT or Discussion Control 6-month Booster Group Session
 
Administer after the Booster Group Session: Two questions on “Amount of fun had” and “Amount learned” [refer to Section 5.5.4]
 

### 6.3.8 Youth Randomized Trial: 12 Month Follow-up Study Visits / Exit Visit

The 12 Month Follow-up Study Visit is targeted to take place on Day 365, counted from the day of the first group session as Day 0, with a targeted window of  $\pm 14$  days and an allowable window of  $\pm 30$  days. This visit is each youth participant's Exit Visit.

Youth 12 Month Follow-up Study Visit Procedures / Exit Visit for Randomized Trial ( $\pm 30$ days)		
Clinical		
 
Obtain targeted medical/medications history per, Section 6.5
 

Behavioral and Counseling		
 
Administer electronic questionnaires - pen and paper may be substituted per Section 10.1:               
 
PHQ-9
 
GAD-7
 
UCLA PTSD exposure screener and reaction index
 
Self-report ART Adherence
 
Barriers to adherence
 
Gender-based Violence (WHO – Victim/Perpetrator)
 
Gender Roles (Rachel Jewkes)
 
AIDS-Related Stigma Scale
 
AIDS Risk Behavior Assessment (Sexual behavior/drug and alcohol use)
 
Children's Report of Parenting Behavior Inventory
 
 
 

Laboratory	Blood	
 
Collect blood for:               
 
HIV-1 RNA (viral load test)
 
Plasma for Inflammatory biomarkers
 
 
 
Hair sample (50-60 strands) for ART concentration – to be collected from the head (scalp) only; not required if participant is bald
 

## 6.4 Caregiver Randomized Trial of Youth TI-CBT

### 6.4.1 Caregiver Randomized Trial: Screening Visit / Entry Visit

Screening and entry procedures may be initiated after written informed consent/assent is obtained. Screening and Entry Visit procedures may be combined into one study visit or split across multiple study visits. Procedures may be conducted on a separate day or on the same day as the caregiver's first group session prior to initiation of the group session. Screening Visit will take place up to 60 days prior to enrollment.

Caregiver Screening Visit / Entry Visit Procedures for Randomized Trial (up to 60 days prior to enrollment)	
Administrative and Regulatory	

• Obtain youth agreement of caregiver participation

• Obtain written informed consent per Section 12.3 and inclusion criterion 4.3.2

• Assign participant identification number (PID)

• Complete eligibility determination and confirmation

• Complete paper-based eligibility checklist, enter checklist data for Step 2 into SES to enroll the caregiver through the same study eligibility checklist linking the PID numbers of the youth and caregiver (randomization based on their youth's randomization), print and file a copy of the confirmation file

Behavioral and Counseling	

• Administer electronic questionnaires - pen and paper may be substituted per Section 10.1: Baseline measures:

○ Demographics

○ AIDS-Related Stigma Scale

○ HIV attitudes and support

○ Barriers to adherence

○ HIV knowledge

○ CBCL caregiver report of youth behavior

### 6.4.2 Caregiver Randomized Trial: Group Session A and B Study Visits

Group Session A and B should be completed within eight weeks of the start of their youth's first group session and will be conducted separately from the youth group sessions. The caregiver Group Sessions A and B will be conducted on separate days.

Caregiver Group Sessions A and B Procedures for Randomized Trial (within 8 weeks of caregiver's youth Group Session 1)	
Behavioral and Counseling	

• Adult study staff delivered caregiver TI-CBT or Discussion Control group session [refer to Section 5.1]

• Administer after the group session: Two questions on "Amount of fun had" and "Amount learned" [refer to Section 5.5.4]

### 6.4.3 Caregiver Randomized Trial: Immediately Post-Last group session Follow-up Study Visit

The Immediate Post-Last group session (IPL) Follow-up Study Visit is targeted to take place immediately following the caregiver Group Session B, either on same day or within a targeted window of up to 14 days and an allowable window of up to 30 days following Group Session B, and in parallel with their respective Youth Follow-up Study Visit.

Caregiver Immediate Post-Last group session (IPL) Follow-up Study Visit Procedures for Randomized Trial (up to 30 days following the Group Session B)	
Behavioral and Counseling	
 
• Administer electronic questionnaires - pen and paper may be substituted per Section 10.1: 
 
○ Participant Intervention Evaluation [refer to Section 5.5.4]
 
○ AIDS-Related Stigma Scale
 
○ HIV attitudes and support
 
○ Barriers to adherence
 
○ HIV knowledge
 
○ CBCL caregiver report of youth behavior
 
 
 

#### 6.4.4 Caregiver Randomized Trial: 6 Month Follow-up Study Visits

The 6 Month Follow-up Study Visit is targeted to take place on Day 182, counted from the day of the caregiver's youth first group session as Day 0, with a targeted window of  $\pm 14$  days and an allowable window of  $\pm 30$  days, and in parallel with their respective Youth Follow-up 6 Month Study Visit.

Caregiver 6 Month Follow-up Study Visit Procedures for Randomized Trial ( $\pm 30$ days)	
Behavioral and Counseling	
 
• Administer electronic questionnaires - pen and paper may be substituted per Section 10.1: 
 
○ AIDS-Related Stigma Scale
 
○ HIV attitudes and support
 
○ Barriers to adherence
 
○ HIV knowledge
 
○ CBCL caregiver report of youth behavior
 
○ Risk for Contamination
 
 
 

#### 6.4.5 Caregiver Randomized Trial: 6 Month Booster Group Session Study Visit

The 6 Month Booster Group Session should take place after completion of the 6 Month Follow-up Study Visit evaluations. For each participant in a group, the booster group session is targeted to take place on the same day (Day 182) as the 6 Month Follow-up Study Visit with a targeted window of up to 14 days and an allowable window of up to 30 days following the 6 Month Follow-up Study Visit.

Caregiver 6 Month Booster Group Session Procedures for Randomized Trial (up to 30 days following the 6 Month Follow-up Study Visit)	
Behavioral and Counseling	
 
• Booster Group Session: Adult study staff delivered caregiver TI-CBT or Discussion Control 6-month Booster group session
 
• Administer after the Booster Group Session: Two questions on "Amount of fun had" and "Amount learned" [refer to Section 5.5.4]
 

#### 6.4.6 Caregiver Randomized Trial: 12 Month Follow-up Study Visits / Exit Visit

The 12 Month Follow-up Study Visit is targeted to take place on Day 365, counted from the day of the caregiver's youth first group session as Day 0, with a targeted window of  $\pm 14$  days and an allowable window of  $\pm 30$  days, and in parallel with their respective Youth 12 Month Follow-up Study Visit. This visit is each caregiver participant's Exit Visit.

Caregiver 12 Month Follow-up Study Visit Procedures for Randomized Trial / Exit Visit for the Randomized Trial ( $\pm$ 30 days)	
Behavioral and Counseling	
 
• Administer electronic questionnaires - pen and paper may be substituted per Section 10.1 
 
○ AIDS-Related Stigma Scale
 
○ HIV attitudes and support
 
○ Barriers to adherence
 
○ HIV knowledge
 
○ CBCL report of youth behavior
 
 
 

## 6.5 Targeted Medical and Medication History

Targeted medical and medication history information, focused on psychiatric history and medication, will be collected per the schedule of evaluations. At each scheduled time point, available medical records will be reviewed and youth and/or their caregivers will be queried on an individual basis in a private setting separate from other participants to ascertain whether the youth have:

- Been diagnosed with a mental illness (if yes, diagnosis and dates of diagnosis)
- Attempted suicide (if yes, number of times; dates of all attempts)
- Received non-study mental health services (if yes, what kind of services; dates provided)
- Received referral from study staff to non-study mental health services (if yes, date and outcome of referral)
- Received psychiatric medications (if yes, medications received and dates of use)

In addition to the above, information on the youth's ART regimen, starting at screening and continuing throughout follow-up, will be ascertained.

All of the above must be source documented in participant study charts and will be entered into eCRFs and/or self-administered electronic questionnaires. Consistent with [Section 7.2](#), occurrences of insomnia, psychiatric disorders, and suicidal ideation or attempt must be adequately source documented and entered into adverse event eCRFs when applicable.

## 6.6 Potential Social Harms

Youth and/or caregiver participants' may experience social harms — non-medical adverse consequences — of their study participation. For example, their involvement in the study could become known to others and they could be perceived as being HIV-infected or their HIV-status may be unintentionally disclosed to others. As a result, participants could be treated unfairly, or could have problems being accepted by their families and/or communities.

Unsolicited youth reported social harms will be source documented and entered into eCRFs. As part of routine study monitoring, social harms will be tabulated and reviewed as described in [Section 7.2](#). Study staff and IYL will make every effort to follow-up with the youth reporting a social harm to determine whether or not the social harm is considered a product of study participation as described in [Section 8](#). Descriptive analyses will be performed as needed to provide information to assist the Protocol Team and study staff with minimizing the occurrence of these events and mitigating their impacts should they occur.

In the event that a participant reports a social harm, every effort will be made by study staff to provide appropriate follow-up support and counseling to the participant as necessary; referrals to

appropriate non-study resources may also be provided. Each site will provide such support in accordance with local standards of care and site SOP's. While maintaining participant confidentiality, study sites may engage their CAB members in exploring the social context surrounding instances of social harms, to minimize occurrence and to identify appropriate follow-up actions be taken.

## **6.7 Additional Procedures for Participants Who Express Suicidal Ideations**

Youth participants who express suicidal ideation during the Pilot Test or Randomized Trial will need to be evaluated for the severity of their risk for suicide. During each session, the IYL taking notes will also note any talk of suicidal or homicidal thoughts or other safety concerns, including social harms. If any of these are mentioned, the IYL will be trained to immediately notify a study staff member. If any response to a self-administered electronic question expresses suicidal or homicidal thoughts or other safety concerns, such as social harms, designated study staff will be notified by email. If the youth poses a risk to self or others, he or she will need to be immediately addressed and treated in accordance with local guidelines and the local standard of care. Such youth may remain on study. Please refer to [Sections 7](#) and [8.1](#).

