Eligibility screening will be initiated after informed consent and assent (if applicable) are provided. As part of the youth informed consent/assent process, youth will be asked whether they are willing to identify a caregiver and provide written permission for the caregiver to participate in the study. Youth who cannot identify a caregiver or do not otherwise provide written permission for caregiver participation remain eligible to enroll as youth can benefit from participation in the intervention without caregivers. If the identified caregiver agrees to participate, they will be introduced to the study and asked to provide informed consent for their own participation. This can be done at any point between youth screening and the first caregiver group session.

Given that each TI-CBT and Discussion Control group should include 6-10 youth per group, sites will need to identify a pool of 12-20 eligible youth to be enrolled/randomized at one time (refer to [Section 6.3.3](#)). Enrollment/randomization must occur within 60 days of each youth participant initiating the screening process. Therefore, sites must screen a sufficient number of potential youth participants within this time period to ensure that 12-20 can be enrolled/randomized on a given

day. The first TI-CBT Intervention and Discussion Control group sessions will be conducted on the day of enrollment/randomization.

Groups will be mixed gender unless a site determines that single gender groups are more appropriate for youth participants during the ADAPT-ITT process. Sites will develop appropriate SOPs accounting for the gender composition and related recruitment process as determined appropriate from the ADAPT-ITT process.

Once a sufficient pool of eligible youth has been identified, the site will schedule the Entry Visit and first group session (the first group session will occur on the day of the Entry Visit). Prior to the Entry Visit, eligible youth will be scheduled for a Pre-Entry Visit to complete baseline evaluations. This visit can occur on the same day or within 14 days prior to the Entry Visit. Youth who are screened more than 60 days prior to enrollment must be re-screened for all inclusion and exclusion criteria prior to enrollment. The youth will not be enrolled if deemed ineligible following repeat of screening evaluations. For details on randomization, refer to [Sections 6.3.3](#) and [9.3](#).

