## **8.1 Monitoring of Youth Mental Health Risk by Study Staff and Indigenous Youth Leaders**

All study staff members, including but not limited to IYL, will be trained to identify and respond appropriately to participants who may experience psychiatric adverse events, social harms, or other issues that require attention.

Staff identifying safety concerns (e.g., youth exhibiting risk of harming themselves or others, youth exhibiting a mental health risk, events resulting in hospitalization or involving suicide attempt) will consult with a designated on-site study clinician who will address the safety concern and intervene as needed to maintain safety of youth and staff. This intervention may include removing the youth from the group for the rest of the session as needed for safety or to minimize disruptive behavior. Staff who learn of safety concerns at a time outside of a session (e.g., youth contacts staff of a safety concern) will have access to standard of care guidelines and lines of communication to consult with designated professionals.

Staff will provide reports from each study arm group session to their supervisors and will refer participants to study clinicians and/or counselors as appropriate in response to potential issues or problems identified during or outside of these sessions. Study clinicians and/or counselors will further evaluate participants to provide appropriate care, treatment, and support that is consistent with their study-specific roles and responsibilities, and according to standard of care.

In addition, all sites must establish adverse event reporting and emergency response SOPs for this study, which will outline procedures, lines of communication, roles, and responsibilities for responding to participants in crisis. All study staff will be trained on these SOPs prior to study initiation and at least annually thereafter throughout the period of study implementation.

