### Standard of care

Youth and caregivers who exhibit or report severe mental health symptoms at any point during the study (e.g., suicidal ideation) will be referred for further evaluation and services as described above and according to the local standard of care. Prior to the Pilot Test, site personnel will create a “standard-of-care resource list” describing the mental health resources and lines of communication available to youth and caregivers at each site to ensure youths’ needs are adequately addressed. This will be true regardless of randomization arm. All referrals to mental health services and outcomes during the 12-month study period will be recorded on eCRFs (refer to [Section 6.5](#)).

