### **Self-administered electronic questionnaires**

Self-administered electronic questionnaires will be completed by youth and caregiver participants using the Medidata Patient Cloud application (app) on a site-provided compatible device (i.e. iPad, iPhone, or Mac). Electronic questionnaires will be translated into local languages prior to study use, as needed. The site will pre-install the app on a device and provide youth and caregiver participants with additional instructions for completing the questionnaires as needed. Youth and caregiver participants will complete the questionnaires at the site with trained research staff present to answer participants' questions or read questionnaire items to participants as needed. If the questionnaires are inaccessible due to environmental interference (e.g., power outages, app not accessible) or any other unforeseen cause, paper versions of the questionnaires will be administered to participants, and the data will be entered by study staff when the app is next accessible.

Refer to [Table 6](#), [Table 7](#), [Table 8](#), and [Table 9](#) below for source and data entry documentation requirements.

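### The protocol's alert for safety answers covers electronic questionnaires only; for the paper fallback the only stated step is later data entry

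*Protocol*

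**What the plan says.** Protocol section 6.7 names two ways in which a safety matter reaches staff. A youth leader who hears it raised in a group session tells a study staff member at once. For questionnaires, the trigger is worded as "If any response to a self-administered electronic question expresses suicidal or homicidal thoughts or other safety concerns", and designated staff are then told by email. No time limit is attached to the email. The section also says that a youth who is a risk to self or others must be dealt with at once.

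Section 10.1 governs how questionnaires are completed. Self-administration on a device at the site is the rule, with trained research staff on hand. Paper is a fallback: "If the questionnaires are inaccessible due to environmental interference", with unforeseen causes of other kinds also admitted. What happens then is stated as follows: "paper versions of the questionnaires will be administered to participants, and the data will be entered by study staff when the app is next accessible". The visit tables in 6.3.5, 6.3.6 and 6.3.8 repeat that paper may be substituted. Those are the post-last-session, 6-month and 12-month visits, and each collects the PHQ-9, GAD-7 and UCLA PTSD-RI.

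**The concern.** The protocol gives safety answers on questionnaires an alert of their own, so it treats them as something to be actively picked up and not left to chance. The alert is tied to the electronic mode. When a site falls back to paper, the protocol puts no equivalent step in its place. A site that follows 10.1 to the letter could collect the form, let the youth go, and first read the answer when entering data after the app is restored.

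What is at stake is the response to an individual youth, not an estimate. The answers in question are foreseeable. Enrolment requires a score at or above the threshold on at least one of the three measures, and the note to 4.1.6 says that suicidal ideation does not exclude a youth. Section 8 requires every psychiatric adverse event to be followed until it resolves or stabilises, but that can start only once someone knows of it.

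**Working it through.** No arithmetic applies, and there is no figure in the plan to reproduce. The check sets the relevant texts side by side and asks, for each, whether it would cause a paper answer to be read before the youth leaves.

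1. **6.7, questionnaire alert.** Limited by its wording to electronic questions. It does not reach paper.
2. **10.1, paper handling.** The one instruction is entry when the app is next accessible. Entering the data might then set off the email. The documents do not say so, and it would come after the delay in any case.
3. **10.1, staff presence.** Trained staff are there to help with questions and to read items aloud if needed. Reviewing completed answers is not part of the stated role.
4. **8.1, training and escalation.** All staff "will be trained to identify and respond appropriately to participants who may experience psychiatric adverse events", and a staff member who identifies a concern consults the on-site clinician. This works in any mode, but it starts from a concern that has already been identified.
5. **8.1, referral to local services.** "Youth and caregivers who exhibit or report severe mental health symptoms at any point during the study (e.g., suicidal ideation) will be referred". A paper answer is a report, but referral depends on someone having read it.
6. **6.5, private history at each follow-up visit.** The listed queries cover diagnoses, suicide attempts, services, referrals and psychiatric medication. Current ideation is not among them. The section does say that "suicidal ideation or attempt must be adequately source documented and entered into adverse event eCRFs when applicable", but this does not explain how an unread paper answer would be found.
7. **Screening.** The three measures decide eligibility under 4.1.6, so paper forms must be scored before enrolment, although no same-day reading is stated. The Pilot Test collects these measures only at screening, and the Pre-Entry visit does not collect them. The gap therefore lies mainly at the three follow-up visits of the Randomized Trial.
8. **Elsewhere.** Sections 7.1 to 7.3, the documentation tables in section 10, Appendix IX and the SAP contain no step for reviewing paper answers.

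Items 1 and 2 establish the gap. Items 4 to 6 show that the duties to act are in place and do not depend on mode. What is missing is the single step of noticing a paper answer in time.

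**The case against.** The strongest reply is that the duty to act does not depend on mode. Section 6.7 opens by requiring any youth who expresses ideation to be evaluated, and 8.1 trains all staff, names a clinician to consult and provides for referral. What remains is who reads the form and when, which is the kind of detail that normally sits in a manual of procedures or a site SOP. Section 8.1 requires every site to have emergency-response SOPs, and 13.3 says that the manual and SOPs guide conduct. None of these was available. This stands in part: the omission is shown for the protocol text only. A reader might infer that the trial has no procedure at all for paper answers, and the documents do not support that.

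A second reply is that the electronic route is not shown to be faster. The email has no deadline, so an electronic answer could also be acted on after the youth has gone. This stands too. A reader might infer that the electronic route guarantees a same-day response and that only paper fails to. The text supports only the narrower contrast that one mode has a stated alert and the other has none.

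Third, the delay is an inference. The protocol does not say when a collected paper form is first looked at, and staff do eventually read each one in order to enter it. That is why the conclusion is that an answer may go unnoticed before the youth leaves, not that it will.

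**Conclusion.** The point holds in a limited form. In the protocol text, the questionnaire alert covers electronic answers only, and the stated handling of paper is later entry. At the post-last-session, 6-month and 12-month visits, a safety answer on paper may therefore not be noticed before the youth leaves. The conclusion rests on the protocol and SAP alone.

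The size cannot be given as a number. The documents state neither how often paper will be used nor how often ideation will be reported at follow-up, and paper is allowed only as a fallback. A reader might try to supply a figure by supposing that one outage puts a whole group on paper and applying the ideation rates quoted in 1.3.3. The documents do not support this. The post-last-session visit is "targeted to take place immediately following the last group session, either on the same day", but the same sentence also allows it up to 30 days later, so a whole group on one day cannot be presumed. The quoted rates are 27% in school-going youth and 42% in youth living with HIV in Soweto. Neither is a follow-up rate in this trial, and the second is referenced to a personal communication.

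Nor does the point touch the planned analyses. Paper answers are still entered, and no power, sample-size or efficacy figure depends on when they are read. It is a cheap improvement for patient safety. It merits action because the consequence of a missed answer is serious and the remedy is small.

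**What to change.** Add one sentence to 6.7, cross-referenced in 10.1: when a questionnaire is completed on paper, the staff member who collects it checks, before the participant leaves, the same items that trigger the electronic alert, and notifies the designated staff or the on-site clinician under 8.1. List the trigger items in the manual of procedures, because the protocol does not name them. Later steps stay as 6.7 and 8.1 already set out. If the two modes are to match, add the same timing to the email sentence. If the manual or site SOPs already contain such a check, a cross-reference to it is enough.

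The cost is the sentence and cross-reference, a short list in the manual, and about a minute of existing staff time per paper form (assumed). There are two downsides. Staff see these answers earlier than they would at data entry. And unless the email sentence is changed as well, the paper rule would carry a time limit that the electronic route lacks.
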